Aim 3: To examine the effect of SM-Mobile, compared to UC and SM, on OSA apnea outcomes (e.g., OSA symptoms and OSA-specific health-related quality of life [HRQOL]). The Epworth Sleepiness Scale scores dropped from baseline to 2-months by 3.4 points and to 4-months by 4.0 points. Given that the cut-off for the ESS is 10 points (above which is considered sleepy; below which is considered within normal limits), all three interventions combined to reduce the sleepiness level of the sample from the sleepy range to the normal limits range (i.e., from mean ESS score of 11.8 to mean ESS score of 8.4 and 7.8 for 2-months and 4-months respectively). The mean ESS scores did not differ significantly between the groups at either the 2-month timepoint (8.3, 8.5, and 8.5 for the 3 groups respectively, UC, SM and SM-Mobile) or the 4-month timepoint (7.9, 7.4, and 8.2 for the 3 groups respectively, UC, SM and SM-Mobile). Sleep quality as measured by the Pittsburgh Sleep Quality Index was also significantly improved across all 3 groups from baseline (mean 11.9) to 2-months (2.8 points, mean 9.1) and to 4-months (2.9 points, mean 9.0). The mean PSQI scores did not differ significantly between the groups at either the 2-month timepoint (8.7, 9.4, and 9.5 for the 3 groups respectively, UC, SM and SM-Mobile) or the 4-month timepoint (8.5, 9.0, and 9.7 for the 3 groups respectively, UC, SM and SM-Mobile).

STATISTICAL ANALYSIS PLAN (SAP):

Data Analytic Plan. Preliminary analyses will begin with an examination of the distribution of variables to assess their characteristics (means, standard deviations, skewness, and kurtosis), to provide descriptive statistics of the study population, and to allow assessment of randomization. Continuous measures will be tested for normality and homogeneity of variance. Non-normally distributed variables will be transformed to meet the normal distribution assumption for linear statistical models.

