The research question in the primary aim 1 will be addressed by comparing the CPAP adherence at post-intervention among the three intervention groups (UC, SM, SM-Mobile) and secondary aims 2 and 3 will be addressed by comparing the three intervention groups (UC, SM, SM-Mobile) on the changes in PACIC, OSA symptoms and OSA HRQOL from pre-intervention to post-intervention. The analytic model is based on an analysis of variance on the post-intervention measure (primary aim) or the change measures (secondary aims). For the change measures, the ANOVA will be accompanied by an analysis of covariance (ANCOVA) on the change scores with intervention as a main effect and the corresponding baseline measurement (baseline PACIC, OSA symptoms and OSA HRQOL) as the covariate. Adjustments will be made to correct for other baseline imbalances between groups, and to adjust for variables known to influence outcome independently of intervention. To explore this, univariate methods will be used. Each of the following variables will be assessed for imbalance between the three intervention groups and their association with each of the outcomes using a univariate analysis (ANOVA, Fisher's exact test or Spearman correlation coefficient as appropriate): age, gender, education and baseline OSA

severity. These variables will be included as covariates in the ANCOVA model if found to be moderately associated ($p < 0.15$) with the outcome under study (CPAP adherence, CAHPS, PACIC, OSA symptoms and OSA HRQOL) or unbalanced ($p < 0.10$) among intervention groups. The outcomes in secondary aims 2 and 3 will also be assessed by the random effects model, which is useful for examining changes in variables from clustered or longitudinal data and allows us to account for all levels of clustering when analyzing the data. It accommodates unequal time intervals and will include all available data, minimizing the effects of missing data on the analyses. The data analytic plan for secondary aim 4, which involves a cost analysis among three interventions [and a calculation of the adherence level per intervention cost], is fully described in section D.7 below. An intent-to-treat analysis will be performed and no correction will be made for multiple comparisons. All above analyses will be performed in R.¹¹⁰ Given below are detailed analysis plans for the primary aim and secondary aims 1 and 2.

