Aim 1: An ANOVA will be used to assess the CPAP adherence at post-intervention among the three groups. Followed will be an ANCOVA by including potential covariates. Any variable that is significantly different at baseline ($p < 0.10$) and found to be associated with response ($p < 0.15$) as well as any clinically significant variables will be included as covariates.

Aim 2: An ANOVA will be used to assess the post vs. pre changes in PACIC among the three groups. An ANCOVA will be performed with treatment as a main effect and baseline score as a covariate. Any variable that is significantly different at baseline ($p < 0.10$) and found to be associated with response ($p < 0.15$) as well as any clinically significant variables will be included as covariates. As a secondary analysis, the change in PACIC will also be evaluated using a random effects model with a group, time and a group-by-time interaction term.

Aim 3: An ANOVA will be used to assess the post vs. pre changes in OSA symptoms and OSA HRQOL among the three groups. An ANCOVA will be performed with treatment as a main effect and baseline score as a covariate. Any variable that is significantly different at baseline ($p < 0.10$) and found to be associated with response ($p < 0.15$) as well as any clinically significant variables will be included as covariates. As a secondary analysis, a random effects model with a group-by-visit interaction term will be used to assess the rate of change in PACIC differs among three intervention groups.

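### The Aim 3 paragraph of the SAP names PACIC, the Aim 2 outcome, for its secondary random effects model instead of OSA symptoms and OSA HRQOL

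*Combined protocol and SAP*

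**What the plan says.** The SAP describes the random effects model at two levels.

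**General section (Data Analytic Plan).** Aims 2 and 3 are to be addressed by comparing the three groups "on the changes in PACIC, OSA symptoms and OSA HRQOL from pre-intervention to post-intervention". Later the section adds: "The outcomes in secondary aims 2 and 3 will also be assessed by the random effects model". It gives a reason for using this model: "It accommodates unequal time intervals and will include all available data, minimizing the effects of missing data on the analyses".

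**Aim-level paragraphs**, which the general section introduces as the detailed plans:

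- Aim 2: after the ANOVA and ANCOVA, "the change in PACIC will also be evaluated using a random effects model with a group, time and a group-by-time interaction term".
- Aim 3: the main analysis is on the Aim 3 outcomes: "An ANOVA will be used to assess the post vs. pre changes in OSA symptoms and OSA HRQOL among the three groups". An ANCOVA with baseline score as covariate follows. The closing sentence then introduces a secondary random effects model with a group-by-visit interaction, which "will be used to assess the rate of change in PACIC differs among three intervention groups".

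**The concern.** The Aim 3 paragraph starts with one set of outcomes and ends with another. A programmer working from it would fit a second longitudinal model to PACIC and none to OSA symptoms or OSA HRQOL.

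This matters because the random effects model is the only planned analysis that the SAP describes as using all available data. The other Aim 3 analyses, ANOVA and ANCOVA on a change score, need both a pre- and a post-intervention value, and the SAP text describes no imputation for them. If the sentence were followed as written, the Aim 3 outcomes would lose the one analysis meant to limit the effect of missing values. They would also lose the one direct test of whether change over visits differs among the groups.

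**Working it through.** No sample size, variance or error rate enters this point, and the plan states no figure to reproduce. The check is a comparison of texts.

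**Step 1: which outcome belongs to which aim.** The Finding section defines Aim 2 by the patient's experience of care, measured by the PACIC. It defines Aim 3 by OSA outcomes, with OSA symptoms and OSA-specific quality of life given as examples. That list is introduced as illustrative, but PACIC does not fit under it: it rates chronic illness care and is the measure named for Aim 2. No part of the document makes PACIC an Aim 3 outcome.

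**Step 2: which outcomes each part of the SAP gives to the random effects model.**

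| Place in the SAP | Outcomes assigned to the random effects model |
|---|---|
| Data Analytic Plan (general) | Those of Aims 2 and 3, listed there as PACIC, OSA symptoms and OSA HRQOL |
| Aim 2 paragraph | PACIC |
| Aim 3 paragraph | PACIC |

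The general section assigns three outcome constructs. The two aim-level sentences name one distinct construct between them, so 3 − 1 = 2 are not named: OSA symptoms and OSA HRQOL. These are constructs, not analysed variables; each may be measured by more than one scale.

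**Step 3: could a second PACIC model be deliberate?** Aim 2 already includes a group-by-time interaction for PACIC, which tests whether change in PACIC differs among the groups. The Aim 3 sentence asks the same question of the same outcome. A second model would add nothing, and no reason for one is given. Carry-over of the outcome name from Aim 2 is the natural explanation.

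**Step 4: do the reported results show what was done?** The Finding section gives group means for sleepiness and sleep quality at 2 and 4 months and says that the groups did not differ significantly at either time. It does not say which model produced those comparisons, and it reports no group-by-visit result. Whether the model was fitted to the Aim 3 outcomes cannot be determined from the document.

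**The case against.** The strongest answer is that the SAP, read as a whole, does plan this model for Aim 3. The general section says so and lists the outcomes, so what remains is one misplaced outcome name whose intended replacement is easy to infer. That stands, and it limits the point to a wrong outcome in the detailed text. It does not remove the point: the aim paragraphs are presented as the detailed plans, and there the operative sentence contradicts both its own paragraph and the general section.

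It is also fair to say that no consequence has been shown. The document gives no dropout or missing-data figure, so the loss from omitting the model cannot be sized. That stands too.

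A reader might infer more than the text supports:

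- *That the SAP has no longitudinal model for the Aim 3 outcomes.* The general section assigns one.
- *That the Aim 3 model omits the group and visit main effects, because only the interaction is named.* Naming the interaction does not exclude the main effects, which are conventionally fitted with it.
- *That the reported Aim 3 comparisons are wrong, or came from a model of PACIC.* Nothing reported shows this.
- *That fitting the model now would be post hoc.* It would be a planned analysis carried out late; only the wording correction and the timing are new.

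**Conclusion.** The point holds as a minor error. The last sentence of Aim 3 names the wrong outcome, contrary to the aim's own outcomes and to the general section of the same SAP. Taken literally, the aim-level plan models PACIC twice and both Aim 3 outcomes not at all.

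The reach is one secondary analysis of a secondary aim. The primary comparison of CPAP adherence, the Aim 2 analyses, and the main Aim 3 ANOVA and ANCOVA are unaffected. No effect on any reported result can be calculated from the document.

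The conclusion assumes that the general section states the intended scope of the model. Steps 1 and 3 of the working support that reading. Confidence that the sentence is wrong as written is high. Whether it affected what was run is unknown.

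**What to change.** In the last sentence of Aim 3, replace PACIC with OSA symptoms and OSA HRQOL.

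Then state whether the model was fitted to those outcomes. If it was, nothing further is needed. If it was not, fit it on the existing data and report it as the analysis already planned in the Data Analytic Plan, citing that section. A short note should say that the Aim 3 wording was corrected and the model run after results were known.

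The cost is a few words in one sentence and, at most, one further analysis step on data already collected.
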